By measuring free-water changes and the integrity of white matter tracts, DTI can indirectly measure changes caused by amyloid plaque deposition (Wen, Risacher, Xie, Li, Harezlak, Farlow et al., 2021; Alexander, Lee, Lazar & Field, 2007; Smith, Johansen-Berg, Jenkinson, Rueckert, Nichols, Miller et al., 2007). The post-NE3107 DTI metric [fractional anisotropy (FA) and mean, axial and radial diffusivity (MD, AD, RD)] image will be subtracted from the baseline image to produce change images (Fu, Shrestha, Sun, Wu, Luo, Zhang, et al., 2019). Neurite orientation dispersion and density imaging (NODDI) uses a three-compartment model to probe brain tissue microstructure: (1) Free Water Fraction (FWF) which estimates the extent of CSF contamination, (2) Neurite Density index (NDI) which quantifies the packing density of axons/dendrites, and (3) Orientation Dispersion index (ODI) which assesses the coherence of neurites (Fu et al., 2019; Zarei, Patenaude, Damoiseaux, Morgese, Smith, Matthews et al., 2010).

Limited literature using NODDI has been produced in-vivo in mild-cognitive impairment subjects, but the current results show it to be more sensitive/robust than traditional FA values (Fu et al., 2019). Similar to ASL, the three indexes will be compared between baseline/follow-up values. It would be expected that an increase in NDI and a decrease in ODI/FWF to correspond with an improvement in brain health (Fu et al., 2019). Here, an established tract-based spatial statistics (tbss) approach will be used to assess the relationship between voxel-wise changes in white matter integrity (Fu et al., 2019). Additionally, graph theory will be applied to quantify the effect of NE3107 on hippocampal connectivity and associate this effect with cross-sectional and longitudinal cognitive performance (Wen et al., 2021). Lastly, probabilistic tractography will be used to simulate white matter connectivity

between the hippocampus formations (Zarei et al., 2010) and Nucleus Basalis of Meynert. The baseline and follow-up will similarly be compared. Again, RMANOVA will compare pre-and post-NE3107 treatment and within group analyses will assess network predictors of response to NE3107 treatment. All imaging analyses will be corrected for multiple comparisons, both across voxel and between analyses.

Arterial Spin Labeling (ASL) data will be processed and analyzed using FSLs Bayesian Inference for ASL MRI (BASIL; Chappell, Groves, Whitcher & Woolrich, 2009; Woolrich, Chiarelli, Gallichan, Perthen & Lie, 2006). ASL scans yield a perfusion image with voxel values representing local perfusion rates; perfusion difference will be calculated (subtracting tagged/control pairs) and averaged to create a mean perfusion-weighted image (Chen, Wolk & Reddin, 2011). Quantification to cerebral blood flow (CBF) values (milliliters of blood per 100 g of tissue per minute) will be implemented using an estimate of the equilibrium magnetization of arterial blood and the mean perfusion values (Ahlgren, Wirestam, Knutsson & Petersen, 2018; Hernandez-Garcia & Jahanian, 2010). Given the variability of ASL across patients, CBF data will be examined as a ratio to mean grey matter signal.

Each participant's ASL data will be linearly registered to each his or her T1-weighted image; images will then be transferred to MNI space using non-linear registration in FSL. Within FSL, a voxel-wise between groups (normal vs MRI) comparison of perfusion, corrected for multiple comparisons, will be performed. A repeated measures comparison within subject for pre-vs post intervention ASL as well as between groups will be used to compare effects of NE3107 to normals. Demographic covariates will be included in the model as indicated. All imaging analyses will be corrected for multiple comparisons, both across voxel and between analyses.

Existing literature consistently demonstrates a dropout of signal seen in the temporal parietal lobes among individuals with dementia of the probable Alzheimer's type (Zhang, Gordon & Goldberg, 2017). The mean perfusion values per voxel in the temporal parietal regions will be measured and used to generate a statistical output of participant values relative to a normative, age-matched database. This will test the hypothesis that there will be either stabilization or improvement of voxel signal among participant scans compared with the normative database associated with NE3107.

Reported trends in BOLD imaging follow dementia progression from earlier stages of decline (e.g., CDR = 0.5, characterized by initial hippocampal hyper connectivity) to progressive stages of dementia (CDR ≥ 1) and ultimate loss of hippocampal connectivity (Wang, Zang, He, Liang, Zhang, Tian et al., 2006; Sperling, 2011). Processing of resting state (rs) fMRI will include correcting for motion artifacts (using framewise displacement calculations, and within-subject independent component analysis), scrubbing, unwarping and spatial smoothing (FWHM = 5mm). rsFMRI data will be linearly registered to stereotaxic MNI space and co-registered with anatomic, T1 data for each participant.

Two approaches will be used to test rs-network differences. First, the hub of the default mode network atlas will be used as a seed region for each subject, and multivariate exploratory linear optimized decomposition into independence components (MELODIC) will be used to

identify the brain regions whose time series correlate significantly with the hub (Erhardt, Rachakonda, Bedrick, Allen, Adali & Calhoun, 2011). Between-groups comparison of these correlation maps will identify differences in default and salience network integrity. A matrix for each subject will then be made from correlations of time series between each node.

Subsequently, ANOVA will be used to assess group comparisons of the connection strength between nodes, within networks and between networks. All of these analyses will be conducted both within diagnostic group (e.g. within healthy control group only) and between diagnostic groups (i.e. compare effects in cognitive impairment and control groups). Finally, time series correlations will be assessed between multiple regions of interest implicated in the literature in Alzheimer's disease (hippocampal formation, Nucleus Basalis of Meynert (NBM), and other seeds) and the rest of the brain to generate functional connectivity maps (Salami, Pudas & Nyberg, 2014; Li, Jia, Qi, Fan, Ma, Ni et al., 2017; Miao, Wu, Li, Chen & Yao, 2011). Then, between-group comparison will identify differences in the connectivity/network integrity of these regions. Finally, within-group regressions will be used to determine which neural network factors predict response to NE3107 treatment. Age, sex, education, and neuropsychological assessment, as needed, will be included as additional regressors. All imaging analyses will be corrected for multiple comparisons, both across voxel and between analyses.

For the seed-based analysis, after spatial normalization of the images, a standard ROI of the bilateral hippocampi will be drawn on the images using a priori anatomic segmentation. A seed reference time course will be obtained by averaging the survived time courses within the ROI. Correlation analyses will be carried out between the seed reference and the whole brain in a voxel-wise manner. The percent signal change will be extracted from within the same ROI across multiple scan acquisitions and compare an individual's change relative to expected levels of change. Existing literature suggests that a relatively higher activation of hippocampal activity precedes a steeper slope of cognitive decline. Individuals with a baseline CDR of 0.5 will typically demonstrate a decrease in fMRI activity in the hippocampus, and individuals with more rapid decline in their neuropsychological testing scores will have higher hippocampal activation at baseline, and the greatest loss of hippocampal activation over time (O'Brien, O'Keefe, LaViolette, DeLuca, Blacker, Dickerson, & Sperling, 2010). We will compare between baseline, pre-NE3107 and post-NE3107.

Further, BOLD-activity changes will be assessed within a standard ROI (e.g., hippocampus; conventionally defined using a priori anatomic segmentation). To do so, the percent signal change within the same ROI across multiple scan acquisitions will be extracted to compare an individual participant's change relative to expected levels of change. The degree of this change will be correlated with NE3107 treatment and other neural network and behavioral changes to further elucidate the intricacies of the NE3107 treatment. A decrease in neurovascular coupling is expected (as shown and evaluated voxel-wise) globally and regionally in the locus coeruleus and temporal parietal lobes compared to age-matched controls. With NE3107 intervention, it is hypothesized that participants will yield improvement in neurovascular response from baseline. This will be analyzed relative to the normative database and expected decline.

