4.2 Inclusion Criteria

In order for a subject to be considered for this study, the following criterion is required:

- Diagnosis of cognitive decline due to degenerative dementia
- Age within range of 50-89 years old
- QDRS score ranging from 1.5-12.5, with a converted Clinical Dementia Rating (CDR) score of 0.5 (mild cognitive impairment) to 1 (mild dementia)

The QDRS scale will be given to all patients; a cutoff range for QDRS scores has been specified as 1.5-12.5 to qualify patients with a clinical dementia score (CDR) of 0.5 to 1.

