5.1.2 Placebo or Control

All participants will receive the study drug; this study will utilize no placebo group.

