5.3 Selection and Timing of Dose for Each Participant

The dose of NE3107 (Biovie, inc.) is 20 mg twice daily (BID) approximately 12 hours apart. The dose will be stable for the duration of the study intervention, and will be the same for all participants.

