5.4 Method of Assigning Participants to Treatment Groups

All participants will receive active study drug at the same dosage.

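### Section 9.5.1 adds control-group, versus-normals and correlated-with-treatment analyses that a single-arm, one-dose, patients-only trial cannot support

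*Combined protocol and SAP*

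**What the plan says.** The design has one arm. Section 5.1.2 states: "All participants will receive the study drug; this study will utilize no placebo group". Section 5.4 adds: "All participants will receive active study drug at the same dosage". Section 5.3 fixes the dose: "The dose will be stable for the duration of the study intervention, and will be the same for all participants". Section 4.2 requires: "Diagnosis of cognitive decline due to degenerative dementia", so a healthy person cannot enrol.

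Section 2.1 lists five primary MRI endpoints, including ASL signal, BOLD functional connectivity and neurovascular coupling. Each is defined against the participant's own baseline.

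Section 9.5.1, the analysis section for those endpoints, plans among other things:

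- **Resting-state BOLD:** all network analyses are to be run within diagnostic group, with "within healthy control group only" as the example, and also between impaired and control groups.
- **ASL:** a within-subject pre/post comparison, and in addition a comparison "between groups will be used to compare effects of NE3107 to normals". A later paragraph treats participants' values relative to a normative database as a test of stabilization or improvement associated with the drug.
- **BOLD activity:** "The degree of this change will be correlated with NE3107 treatment", and, in the same sentence, with other network and behavioural changes.

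The section also says that all imaging analyses are corrected for multiplicity between analyses as well as across voxels.

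**The concern.** Three of the planned analyses need something the trial does not have: a healthy control group, a group in which an NE3107 effect can be contrasted with normals, or participants who differ in treatment. As written, an analyst either cannot run them or must substitute data the plan does not specify.

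If unspecified norms are substituted, the output answers a different question. It describes how patients differ from healthy people, yet it sits under the primary-endpoint heading and, for ASL, is described as a test of benefit. A disease difference could then be reported as evidence about the drug.

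Leaving uninformative or inestimable tests in the family corrected between analyses also makes that correction ill-defined, or takes power from the valid tests, with about 20 completers expected.

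**Working it through.** **1. Who is in the data.** Section 9.2 plans about 25 participants to give at least 20 completers at 20% attrition: 20 / (1 − 0.20) = 25, which reproduces. All 25 are patients, so the number of enrolled healthy controls is 0. An analysis within healthy controls has no trial data, and an impaired-versus-control ANOVA has none on one side.

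**2. Correlation with treatment.** Let x be assigned treatment, equal to 1 for all 20 completers, and y the BOLD change.

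- r = Σ(x − x̄)(y − ȳ) / √[Σ(x − x̄)² · Σ(y − ȳ)²]. Every x − x̄ is 0, so r = 0/0, which is undefined.
- In regression form, the design matrix with an intercept and treatment has rank 1 of 2, so the treatment coefficient cannot be estimated.

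**3. What a comparison with external normals shows.** Section 9.5.1 mentions published normals for the cognitive Z-scores and a normative database for ASL and neurovascular coupling. It gives no size, scanner match or repeat scans for the imaging norms, and does not say that the resting-state control group is that database. Suppose it is used, there is no drug effect, and patients lie D SD below normal (D is assumed; the documents give none). For a two-sided t test at 0.05 with 20 patients and M normals, the noncentrality is D / √(1/20 + 1/M):

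| D | M = 20 | M = 100 | M = 1000 |
|---|---|---|---|
| 0.5 | 0.34 | 0.53 | 0.60 |
| 1.0 | 0.87 | 0.98 | 0.99 |

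These are probabilities of a significant difference when the drug does nothing.

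**4. Norms used only to rescale.** If both visits are scored against one fixed norm (mean μ, SD σ), the change is (y₂ − μ)/σ − (y₁ − μ)/σ = (y₂ − y₁)/σ. The norm mean cancels and the paired t statistic is unchanged. This use is harmless, but it is simply the within-patient test.

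**5. Reading visits separately against a norm.** With no true change, n = 20, a one-sample t test against a fixed norm at each visit, and an assumed test-retest correlation of 0.6 to 0.8, the simulated chance that a difference significant at baseline is non-significant at follow-up is:

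| Assumed deficit | Conditional on baseline significance |
|---|---|
| 0.3 SD | about 34–48% |
| 0.5 SD | about 18–27% |
| 0.8 SD | about 4–5% |
| 1.0 SD | about 1% |

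The figure depends almost wholly on the assumed deficit, so it illustrates a hazard and does not estimate one.

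**6. What the valid tests can do.** A paired test at n = 20 can be run. Assuming a non-drug shift of 0, 0.25 or 0.5 SD of change, it is significant with probability 0.05, 0.19 or 0.57. It tests change; it does not separate drug from time or retest effects.

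**The case against.** The strongest reply is that these analyses are additions. The primary endpoints are defined as change from baseline, and Section 9.5.1 plans tests that fit: repeated-measures ANOVA from baseline to completion, Wilcoxon signed-rank for glutathione, within-subject pre/post ASL, and a pre- versus post-NE3107 comparison of the BOLD seed analysis. **This stands.** A reader might infer that the primary analysis as a whole cannot be run; the documents do not support that.

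Second, external normative data are named, so some comparisons with normals could run. **This stands too**, and it would be wrong to say that no comparator data exist. The gap is that the dataset is not specified and the resting-state control group is not linked to it.

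Third, one might infer that the norms contain a single time point, so that normal change could not be known. The documents do not say this. Section 9.5.1 refers to expected levels of change and expected decline. What can be said is that no 3-month repeat scans in normals are described.

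Fourth, treatment might mean exposure: capsule counts (Section 5.8) can vary between patients. But the sentence in Section 9.5.1 does not define treatment that way, and assigned dose is constant. The same sentence also plans correlations with network and behavioural changes, which can be estimated and should not be lost.

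Finally, the plan states no rule that losing a baseline difference from normal counts as response. The table in step 5 of the working shows what could go wrong if results were read that way, not something the plan commits to.

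**Conclusion.** The point holds in limited form. Section 9.5.1 is wrong as written where it calls for an analysis within healthy controls (0 enrolled) and a correlation with assigned treatment (0/0). Both follow from the design without any numerical assumption. The impaired-versus-control and NE3107-versus-normals comparisons can run only on external data not adequately specified in the plan, and then show a patient-versus-normal difference. The 0.34 to 0.99 range for a significant result with no drug effect rests on an assumed deficit of 0.5 to 1.0 SD and 20 to 1000 normals.

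The within-patient tests survive and can carry the primary endpoints. Their inability to separate drug from time is a consequence of the declared open-label, single-arm design, and removing the normative comparisons does not cure it. The text should be corrected before analysis because it sits under the primary-endpoint heading.

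**What to change.** Amend Section 9.5.1 as follows:

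1. Delete the resting-state analysis within a healthy control group.
2. Delete the correlation of BOLD change with NE3107 treatment. Keep the correlations with other network and behavioural changes, labelled exploratory.
3. State that each primary MRI endpoint is tested only as within-participant change from baseline.
4. Keep any patient-versus-normal comparison, including the impaired-versus-control and ASL ones, as descriptive only. Name the external dataset (source, size, scanner, matching, and whether repeat scans exist) and state that these comparisons are not used for efficacy and are not counted in the multiplicity family. Reword the ASL paragraph that presents the normative comparison as a test of stabilization or improvement.

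The cost is wording. Enrolment, scanning and data collection do not change, and no estimable analysis is lost.

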9 PLANNED STATISTICAL METHODS

9.1 General Considerations

Statistical analyses will be performed by the statistician on staff with The Regenesis Project. Software for statistical analyses will include Microsoft Excel (version 14 or newer) and IBM SPSS Statistics for Windows, version 26 (IBM Corp., Armonk, N.Y., USA). Statistical analyses will be run to compare change from baseline at the post-intervention termination follow-up (three months after baseline) using a level of significance of 0.05.

A single unblinded interim analysis may be performed when 30% to 50% of the participants have completed the final follow-up timepoint. The purposes of this interim analysis are to declare futility, study discontinuation for overwhelming efficacy, or sample size re-estimation. The sample size will not be reduced based on interim data.

The primary analysis model for the efficacy endpoints will be an MMRM analysis. All available data will be included in these models with no imputation for missing data. Supportive analyses of efficacy data may be conducted to evaluate different methods of handling missing data (i.e., Last Observation Carried Forward, Baseline Observation Carried Forward, multiple imputation for missing data, etc.). These supportive analyses will be detailed in the SAP. Each endpoint within the neuropsychological testing family will be analyzed using MMRM analysis methods in a similar manner as to how the primary endpoints will be analyzed. Formal significance for a given hypothesis will only be declared if that hypothesis is significant and all hypotheses within the family preceding it are significant. This approach will ensure strong type 1 error control is present for all statistical tests conducted.

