9.2 Determination of Sample Size

Approximately 25 participants are expected to be enrolled in this Phase II trial to evaluate longitudinal findings from multimodal MRI among the population that is being studied. The study population is sufficiently broad and the conditions of interest are sufficiently prevalent so that recruitment of participants is not a limiting factor for the trial site.

The sample size was chosen according to a power analysis calculated with 80% power and a significance level of 0.05. To achieve completion data for at least 20 participants, enrollment of 25 participants will allow for 20% attrition while maintaining statistical integrity.

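### With one arm and one dose, the planned within-group regressions can show which network factors go with change during treatment, not which predict response to NE3107

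*Combined protocol and SAP*

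**What the plan says.** The BOLD part of Section 9.5.1 states that "within-group regressions will be used to determine which neural network factors predict response to NE3107 treatment". The DTI-NODDI part says that "within group analyses will assess network predictors of response to NE3107 treatment". Neither sentence defines response, and neither says when the network factor is measured.

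Section 5.1.2 states: "All participants will receive the study drug; this study will utilize no placebo group". Section 5.4 adds: "All participants will receive active study drug at the same dosage".

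On the natural course of disease, the seed-based BOLD text in Section 9.5.1 says: "Existing literature suggests that a relatively higher activation of hippocampal activity precedes a steeper slope of cognitive decline". It goes on to say that faster decliners start with higher hippocampal activation and lose the most of it. Section 9.5 expects 4-9% of participants to progress over the three months.

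Section 9.1 sets the tests "using a level of significance of 0.05", with no sidedness given.

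**The concern.** Asking whether a factor predicts response to a drug is asking whether the drug's effect differs across levels of that factor. That needs a contrast in exposure: treated against untreated, or one dose against another. This trial has neither. What the regression tests is whether the factor is related to change from any cause, and a factor can be related to change without any drug effect.

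At stake is a conclusion about who benefits. A connectivity or activation feature that marks only prognosis, or only a noisy first scan, could be reported as a predictor of benefit from NE3107 and then used to select patients for a later study.

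**Working it through.** **1. The plan's own figure.** Section 9.2 cites a power analysis "calculated with 80% power and a significance level of 0.05" and enrols 25 "To achieve completion data for at least 20 participants" after 20% attrition. The arithmetic holds: 20 / (1 - 0.20) = 25. No figure is given for the predictor regressions, so N = 20 is used below.

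**2. What the slope estimates.** Write each patient's change as N + D + E, where N is the change that would have occurred untreated, D is the drug effect, and E is follow-up minus baseline measurement error. For a factor X,

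slope = [Cov(X,N) + Cov(X,D) + Cov(X,E)] / Var(X).

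The question concerns Cov(X,D) alone, but a single arm identifies only the sum. In a concurrent untreated arm the slope would be [Cov(X,N) + Cov(X,E)] / Var(X), and the difference between the two slopes would isolate the drug term. As a check, with zero drug effect, a factor-by-treatment interaction test rejects 4.8-4.9% of the time with 10 per arm and 4.9-5.5% with 20 per arm. The settings were reliability 0.7 and prognostic correlation 0.4.

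**3. Assumptions for the illustration.** Zero drug effect (D = 0), normal data, a two-sided test (assumed), no covariates and no multiplicity correction. At least 100,000 simulated trials were run per setting. The documents give neither a prognostic correlation nor a test-retest reliability, so both are assumed and ranged.

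**4. Prognostic factor: Cov(X,N) not zero, no shared error.** With rho the correlation between the factor and natural change, N = 20:

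| rho | rejects at 0.05 | rejects at 0.01 |
|---|---|---|
| 0 | 5% | 1% |
| 0.1 | 7% | 2% |
| 0.2 | 13% | 4% |
| 0.3 | 25% | 9% |
| 0.4 | 43% | 20% |

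**5. Shared scan error: Cov(X,E) not zero.** This arises only if a measure's change is regressed on its own baseline. Let baseline b = T + e1 and follow-up f = T + e2, with unit variance and reliability R. Then Cov(b, f-b) = -(1-R) and Var(f-b) = 2(1-R), so

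corr(b, f-b) = -sqrt((1-R)/2).

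| R | correlation | rejects at 0.05 | rejects at 0.01 |
|---|---|---|---|
| 0.5 | -0.50 | 64% | 38% |
| 0.7 | -0.39 | 40% | 18% |
| 0.8 | -0.32 | 28% | 11% |
| 0.9 | -0.22 | 16% | 5% |

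**6. Do the plan's safeguards remove it?**
- *Covariates.* Section 9.5.1 allows age, sex, education and neuropsychological assessment. With four covariates in the own-baseline case (one assumed correlated 0.3 with the true value), rejection is still 55, 36 and 14% at R = 0.5, 0.7 and 0.9.
- *Multiplicity correction.* It lowers the threshold but protects against the wrong null, no association with change. The 0.01 columns (0.05 / 5, as if five tests were corrected by Bonferroni) still exceed 1% whenever rho or the shared error is not zero.
- *Healthy and normative comparisons.* Section 9.5.1 mentions these, but ties none to the predictor regressions. None is described as untreated dementia patients rescanned at three months, which is what would supply natural change by baseline factor.

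**The case against.** The strongest reply is that the plan does not write the worst-case analysis. Neither sentence mentions baseline or change. Response could mean clinical response, as in Section 9.4, or a cognitive score judged against a minimal important difference, as in Section 9.5.2. An MRI factor set against a cognitive score shares no scan error, so regression to the mean of the kind in step 5 would not arise. This stands. A reader might infer that the plan regresses a measure's change on its own baseline and so carries a false-positive rate of up to 64%. The documents do not support that: they do not specify that regression, although they do not exclude it.

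A reader might also infer that the regression rejects too often whatever the factor. It does not: a factor that is neither prognostic nor shares error with the outcome rejects at 5%. The text on hippocampal activation gives no correlation and no 3-month horizon. Progression of 4-9% is only 0.8 to 1.8 of 20 completers, so the documents lend no support to correlations as high as 0.4. The uncorrected rates are also not those of the planned, corrected test.

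Finally, the lack of a control group is openly stated, and these analyses are neither among the five primary imaging endpoints nor among the secondary endpoints. That limits the consequence. It does not make the sentences right: disclosing an open-label design does not allow a single arm to determine predictors of drug response.

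**Conclusion.** The point holds as a matter of what the design can identify, and that part needs no assumed number. With one arm, one dose and no placebo, the regressions in Section 9.5.1 cannot tell prediction of drug effect from prognosis or, where scan error is shared, from regression to the mean. The plan itself describes one network factor as prognostic, so the confusion is not hypothetical.

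The size is conditional. It runs from no excess for an unrelated factor to 43% at an assumed prognostic correlation of 0.4, at N = 20 and an uncorrected two-sided 0.05. The own-baseline rates of 16-64% apply only if that unstated regression is run. The damage is confined to claims about who responds; the primary pre/post tests are not touched by this point.

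**What to change.** In the BOLD and DTI-NODDI parts of Section 9.5.1:
- Replace the language of predicting response to NE3107 with *are associated with 3-month change during treatment*.
- Define the outcome and the time at which each network factor is measured.
- State that these regressions are exploratory and cannot distinguish drug response from prognosis or regression to the mean.
- State that a regression of a measure's change on its own baseline will not be interpreted as prediction of response.

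The sentence in Section 9.4 relating baseline CDR to strength of clinical response needs the same caveat.

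Regressing change on the mean of the two visits (Oldham's method) is not a repair. Its regressor contains the 3-month value, so it is not a baseline predictor. It also fails under natural loss proportional to the true baseline: with zero drug effect and N = 20, assumed losses of 20, 30 and 40% give rejection of about 12, 21 and 32% at reliability 0.7, and 39, 68 and 87% at 0.9.

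The cost is a few sentences, with no new data, visits or participants. The downside is a less attractive claim. Identifying predictors of drug response would need a concurrent untreated arm and a factor-by-treatment interaction test, which this trial does not have.
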